2.0 TRIAL DESIGN

2.1 Trial Design

This is a single center, open label trial of pembrolizumab in patients failing to respond to or relapsing after anti-CD19 chimeric antigen receptor modified T cell therapy (CTL019/CTL119) for relapsed or refractory CD19+ lymphomas.

Eligible patients will have CD19+ diffuse large B-cell, follicular, or mantle cell lymphomas with no available curative treatment options, a limited prognosis of several months to <2 years anticipated survival with currently available therapies, and progressive or relapsed disease after a single intravenous dose of $5 \times 10^8 \pm 20\%$ CTL019/CTL119 administered on our currently enrolling clinical trial (NCT02030834). We anticipate enrollment of 12 total patients onto the present trial for patients not responding to, or relapsing after, CTL019/CTL119.

[figure not shown]
The safety and efficacy of pembrolizumab in this group of patients will be determined using a fixed dose of 200mg IV. This dose was previously well-tolerated and effective for treatment of patients with metastatic melanoma and NSCLC. The primary safety endpoint will be determined by assessing the rate of pembrolizumab discontinuation as well as the rate of occurrence of treatment-related adverse events (AEs), defined as NCI CTCAE version 5 grade ≥ 3 AEs are possibly, probably, or definitely related to study treatment or grade 4 cytokine release syndrome. Secondary efficacy endpoints will be assessed, including overall response rate (ORR) and progression-free survival (PFS).

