³“All other immune-related AEs” excludes hematologic AEs given that hematologic changes are not considered reportable AEs or treatment-limiting toxicity (Section 7.3, Section 8.1). For grade 3-4 hematologic toxicity at least possibly related to therapy, therapy will be held until toxicity resolves to grade 0-1 or subject’s baseline.

NOTE:

For participants with Grade 3 or 4 immune-related endocrinopathy where withhold of pembrolizumab is required, pembrolizumab may be resumed when AE resolves to \leq Grade 2 and is controlled with hormonal replacement therapy or achieved metabolic control (in case of T1DM).

This document is confidential and the property of the University of Pennsylvania. No part of it may be transmitted, reproduced, published, or used by other persons without prior written authorization from the regulatory sponsor.

Dose modification for cytokine release syndrome:

If patients develop cytokine release syndrome grades 1-3 after pembrolizumab, then pembrolizumab will be held until cytokine release syndrome resolves. Once cytokine release syndrome has fully resolved, the clinical investigator has the option of restarting pembrolizumab at ½ dose (100mg) every 3 weeks. If patients develop grade 4 cytokine release syndrome or require administration of tocilizumab, pembrolizumab will be stopped due to drug toxicity.

Dosing interruptions are permitted in the case of medical / surgical events or logistical reasons not related to study therapy (e.g., elective surgery, unrelated medical events, patient vacation, and/or holidays). Subjects should be placed back on study therapy within 3 weeks of the scheduled interruption, unless otherwise discussed with the Principal Investigator and the Data and Safety Monitoring Board. The reason for interruption should be documented in the patient's study record.

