Tocilizumab should be used as a weight-based dose of 8 mg/kg at the time of hemodynamic instability. This management approach is designed to avoid life-threatening toxicities, while attempting to allow the CART-19 cells to establish a proliferative phase that appears to correlate with anti-tumor efficacy. Thus, the timing of the tocilizumab should be individualized, in close consultation with the Principal Investigator and/or expert consultants for the trial. Steroids have not always been effective in this setting and may not be

This document is confidential and the property of the University of Pennsylvania. No part of it may be transmitted, reproduced, published, or used by other persons without prior written authorization from the regulatory sponsor.

necessary given the rapid response to tocilizumab. Because steroids will interfere with CART-19 function and efficacy, if used, they should be rapidly tapered.

Upon developing the prodrome of high-persistent fevers following CART-19 infusion, patients should then be followed closely. Infection and tumor lysis syndrome work up should be immediately undertaken. The pharmacy should be notified of the potential need for tocilizumab. Patient management in an intensive care unit may be required and the timing is dependent upon local institutional practice. In addition to supportive care, tocilizumab may be administered in cases of moderate to severe CRS, especially if the patient exhibits any of the following:

- Hemodynamic instability despite intravenous fluid challenges and moderate stable vasopressor support
- Worsening respiratory distress, including pulmonary infiltrates, increasing oxygen requirement including high-flow O₂, and/or need for mechanical ventilation.
- Any other signs or symptoms of rapid deterioration despite medical management

The recommended dosing for tocilizumab is 8 mg/kg i.v. single dose. Not all Grade 4 CRS reactions following CART-19 have been immediately treated with tocilizumab and decisions are, in part, based upon the rapidity of the syndrome onset and underlying patient reserve.

Other anti-cytokine therapies, such as repeat administration of tocilizumab or use of siltuximab or etanercept, may also be considered if the patient does not respond to the initial dose of tocilizumab. If the patient experiences ongoing CRS despite administration of anti-cytokine directed therapies, anti T-cell therapies such as Cytosan, ATG, Campath may be considered.

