Mild reaction: Treated with supportive care such as anti-pyretics, anti-emetics	Moderate reaction requiring IV fluids or parenteral nutrition; some signs of organ dysfunction (i.e. grade 2 creatinine or grade 3 liver function tests ([LFTs] related to CRS and not attributable to any other condition). Hospitalization for management of CRS related symptoms including fevers with associated neutropenia.	More severe reaction: Hospitalization required for management of symptoms related to organ dysfunction including: 
 • grade 4 LFTs • grade 3 creatinine related to CRS and not attributable to any other conditions • hypotension requiring multiple fluid boluses for blood pressure support or low-dose pressors (see Table 7.2.5b) • coagulopathy requiring fresh frozen plasma or cryoprecipitate • hypoxia requiring supplemental oxygen (nasal cannula oxygen, high flow oxygen, Continuous Positive Airway Pressure [CPAP] or Bilateral Positive Airway Pressure [BiPAP]) Patients admitted for management of suspected infection due to fevers and/or neutropenia may have grade 2	Life-threatening complications such as hypotension requiring high-dose pressors (see Table 7.2.5b) or hypoxia requiring mechanical ventilation	Death

This document is confidential and the property of the University of Pennsylvania. No part of it may be transmitted, reproduced, published, or used by other persons without prior written authorization from the regulatory sponsor.

Table 7.2.5a - CRS Toxicity Grading				
		CRS and this excludes management of fever or myalgias		

Table 7.2.5b High Dose Vasopressor Use

Definition of “High-Dose” Vasopressors	
Vasopressor	Dose for ≥ 3 hours
Norepinephrine monotherapy	≥ 20 mcg/kg/min
Dopamine monotherapy	≥ 10 mcg/kg/min
Phenylephrine monotherapy	≥ 200 mcg/min
Epinephrine monotherapy	≥ 10 mcg/min
If on vasopressin	High-dose if vaso + Norepinephrine Equivalent (NE) of >10 mcg/min (using Vasopressin and Septic Shock Trial (VASST) formula)
If on combination vasopressors (not vasopressin)	Norepinephrine equivalent of ≥ 20 mcg/min (using VASST formula)

Vasopressin and Septic Shock Trial (VASST) Equivalent Equation:

$$\text{Norepinephrine equivalent dose} = [\text{norepinephrine (mcg/min)}] + [\text{dopamine (mcg/kg/min)} \div 2] + [\text{epinephrine (mcg/min)}] + [\text{phenylephrine (mcg/min)} \div 10]$$

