8.0 STATISTICAL ANALYSIS PLAN

8.1 Statistical Analysis Plan

8.1.1 Primary Objectives & Hypotheses

(1) Objective: To determine the safety of pembrolizumab in patients failing to respond to or relapsing after anti-CD19 chimeric antigen receptor modified T cell therapy for relapsed or refractory CD19+ lymphomas. Safety will be assessed by adverse event monitoring. Patients who have received at least one dose of pembrolizumab will be considered evaluable for safety. In this trial, success will be defined as receiving at least one dose of pembrolizumab and the lack at least possibly related adverse events leading to permanent discontinuation of pembrolizumab. Patients who experience Grade 3 or higher non-hematologic toxicity leading to permanent pembrolizumab discontinuation or any Grade 4 non-hematologic toxicity or cytokine release syndrome at least possibly related to pembrolizumab will be considered toxicity failures.

Methodology: We will use a Bayesian monitoring rule to assure that the failure rate is no greater than 30%. Monitoring will begin with the first patient. Because little information is available on the safety of this drug in lymphoma, we will assume a non-informative Beta(1, 1) prior distribution for the failure rate. We will denote the rate of pembrolizumab discontinuation as failure rate, FR, and will use the following monitoring rule in the interest of patient safety: we will stop the trial if at any time: $\Pr[\text{FR} > 0.30 \mid \text{data from the trial}] \geq 97.5\%$

That is, if at any time during the study, we can conclude that there is at least a 97.5% chance that the failure rate is greater than 30%, we will stop the study. The stopping boundaries corresponding to this probability criterion are to terminate the trial if:

$(\# \text{ of patients that experience failure}) / (\# \text{ of patients evaluated}) \geq 3/3, 3/4, 4/5, 4/6, 5/7, 5/8, 6/9, 6/10, 7/11, 7/12$. Any patient who has received at least one dose of pembrolizumab will be included in this denominator for evaluable patients if they have received at least 4 doses of pembrolizumab and not experienced toxicity OR if they have experienced any toxicity with any dose of pembrolizumab.

If the study is not terminated early, it will continue until all patients have been treated with pembrolizumab and completed all follow up evaluations.

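### The norepinephrine-alone cut-off in Table 7.2.5b is in mcg/kg/min while the rest of the table counts norepinephrine in mcg/min, so Grade 4 CRS can be graded 3

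*Combined protocol and SAP*

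**What the plan says.** Section 7.3.3 replaces the CTCAE grading of CRS with its own scale, Table 7.2.5a, and defines high-dose vasopressors in Table 7.2.5b as a dose held for at least 3 hours.

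Table 7.2.5a refers to Table 7.2.5b on both sides of the Grade 3/4 line:
- Grade 3 includes "hypotension requiring multiple fluid boluses for blood pressure support or low-dose pressors (see Table 7.2.5b").
- Grade 4 is "Life-threatening complications such as hypotension requiring high-dose pressors (see Table 7.2.5b) or hypoxia requiring mechanical ventilation".

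Within Table 7.2.5b:
- Norepinephrine alone is high-dose at 20 mcg/kg/min or more.
- With vasopressin the rule is "High-dose if vaso + Norepinephrine Equivalent (NE) of >10 mcg/min".
- For other combinations it is "Norepinephrine equivalent of ≥ 20 mcg/min (using VASST formula").
- The equation under the table adds norepinephrine in mcg/min with no multiplier.

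The grade then drives three other parts of the plan:
- Section 5.2.1.2: "If patients develop grade 4 cytokine release syndrome or require administration of tocilizumab, pembrolizumab will be stopped due to drug toxicity". After CRS of Grade 1 to 3 the drug is held, and the investigator may restart it at 100 mg once the syndrome has resolved.
- Section 2.1 names the event in the primary safety definition: "definitely related to study treatment or grade 4 cytokine release syndrome".
- Section 8.1.1 does so in the failure definition: "any Grade 4 non-hematologic toxicity or cytokine release syndrome at least possibly related to pembrolizumab will be considered toxicity failures".

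**The concern.** One drug has two cut-offs in one table, in units that differ by a factor of body weight. They agree only for a patient who weighs 1 kg. The row for norepinephrine alone is the one out of line, and it errs towards under-grading.

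Two things are at stake. The first is the patient: someone with CRS and shock on norepinephrine alone could be graded 3 and become eligible for re-exposure at half dose, when the plan means to stop the drug. The second is the primary safety result: the same patient could be left out of the failure count that the Bayesian stopping rule monitors. In a trial of 12, one patient can decide which side of the 30% limit the result falls on.

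**Working it through.** **Inputs from Table 7.2.5b and its equation**

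Norepinephrine equivalent (NE, mcg/min) = norepinephrine (mcg/min) + dopamine (mcg/kg/min) ÷ 2 + epinephrine (mcg/min) + phenylephrine (mcg/min) ÷ 10.

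Combination cut-off: NE of 20 mcg/min.

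**Assumption.** The documents give no body weights. I use 50, 70 and 100 kg.

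**Step 1. Put each single-drug cut-off on the NE scale.**

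| Drug alone | Printed cut-off | NE (mcg/min) |
|---|---|---|
| Phenylephrine | 200 mcg/min | 200 ÷ 10 = 20 |
| Epinephrine | 10 mcg/min | 10 |
| Dopamine | 10 mcg/kg/min | 10 ÷ 2 = 5 |
| Norepinephrine, as printed, 50 kg | 20 mcg/kg/min | 20 × 50 = 1,000 |
| Norepinephrine, as printed, 70 kg | 20 mcg/kg/min | 20 × 70 = 1,400 |
| Norepinephrine, as printed, 100 kg | 20 mcg/kg/min | 20 × 100 = 2,000 |
| Norepinephrine, read as mcg/min | 20 mcg/min | 20 |

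The other three rows lie between 5 and 20. The printed norepinephrine row is 1,000 ÷ 20 = 50, 1,400 ÷ 20 = 70 and 2,000 ÷ 20 = 100 times the combination cut-off. Read in mcg/min it equals both the combination cut-off and the phenylephrine row. Dopamine is per kg in its row and in the equation, so it is consistent.

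**Step 2. Convert the other way.** 20 mcg/min is 20 ÷ 50 = 0.40, 20 ÷ 70 = 0.29 and 20 ÷ 100 = 0.20 mcg/kg/min.

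**Step 3. Grade one patient of 70 kg.**
- Norepinephrine 30 mcg/min alone: 30 ÷ 70 = 0.43 mcg/kg/min, and 0.43 ÷ 20 = 2.1% of the printed cut-off. Not high-dose, so the Grade 3 wording applies.
- The same dose plus phenylephrine 10 mcg/min: NE = 30 + 10 ÷ 10 = 31. High-dose, so Grade 4.
- The same dose plus vasopressin: 30 exceeds 10. High-dose, so Grade 4.

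A small second pressor changes the grade, while the norepinephrine dose itself does not.

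**Step 4. Effect on the failure rate.** One patient in 12 is 1 ÷ 12 = 8.3 points. Four failures give 4 ÷ 12 = 33%, above the 30% limit; with one missed, 3 ÷ 12 = 25% is below it.

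**Step 5. How often it could arise.** The documents give no rate of CRS after pembrolizumab. If a share p of patients had norepinephrine-only CRS of this kind, the chance of at least one among 12 is 1 − (1 − p)^12: 11% for p = 1%, 46% for 5% and 72% for 10%. These values of p are assumptions for illustration only. They do not deduct cases caught by other safeguards, and the finding does not depend on them.

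**The case against.** The case against does not dispute the mismatch; it argues that it would rarely do harm.

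- **The slip is obvious.** A cut-off above 1,000 mcg/min sits beside one of 20, and the Grade 4 cell gives its criteria as examples, so an investigator can grade higher on judgment. True, but a grading definition should not depend on being overridden.
- **Tocilizumab.** Section 5.4.2 recommends it for moderate to severe CRS and at hemodynamic instability, and any use stops pembrolizumab whatever the grade. This will catch many such patients. It is not complete: the section leaves timing to individual judgment and records that "Not all Grade 4 CRS reactions following CART-19 have been immediately treated with tocilizumab". That sentence concerns timing after CAR-T infusion and does not show that patients went untreated, so it is only limited evidence of a gap.
- **Independent checks.** Table 6 in Section 7.3.2 requires advance approval by a clinical monitor for rechallenge after a serious event that the drug may have caused, and CRS that needs hospital care is serious under Section 7.2.3.1. Under Section 10.4 the medical monitor reviews grading. Both checks are real, but the monitor would be checking against the same faulty table.
- **Other routes to the endpoint.** Mechanical ventilation gives Grade 4 by itself. A Grade 3 event that leads to permanent discontinuation still counts as a failure. Section 2.1 also counts related CTCAE Grade 3 or higher events, so the event would probably remain visible there.
- **Ambiguous failure wording.** The sentence in Section 8.1.1 can be read as counting CRS of any grade. On that reading the Grade 3/4 line does not affect the failure count. Section 2.1 specifies Grade 4, which makes the narrower reading the natural one, and the dosing rule in Section 5.2.1.2 depends on grade either way.

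What stands is that the exposed group is narrow: patients on norepinephrine alone, without ventilation or tocilizumab, not graded up on judgment or corrected on review, and held or restarted rather than discontinued.

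**Conclusion.** The concern holds. The norepinephrine-alone cut-off conflicts with the combination row, the vasopressin row and the equation of the same table, and at 50 to 100 kg it is 50 to 100 times the combination cut-off. As printed, it makes the norepinephrine-only route to Grade 4 unusable in practice. The mismatch is certain; that mcg/min was the intended unit is an inference from the rest of the table. The expected frequency is unknown and is reduced by the safeguards. The consequences for an affected patient are possible re-exposure to pembrolizumab after severe CRS and, if Section 8.1.1 is read as counting Grade 4 CRS, a missed failure in the primary safety analysis. This should be corrected, although it does not undermine the design.

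**What to change.** In Table 7.2.5b, change the norepinephrine-alone row to at least 20 mcg/min, after the sponsor's clinicians have confirmed the value. Leave dopamine in mcg/kg/min, as the equation requires. Re-check the grade of any CRS event already recorded in a patient who received norepinephrine alone, and correct the dosing decision and failure status if the grade changes. The cost is one table cell and a short review of graded events; design, sample size and analysis stay the same.

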7.3.2 Evaluating Adverse Events

An investigator who is a qualified physician will evaluate all adverse events according to the NCI Common Terminology for Adverse Events (CTCAE), version 5.0. Any adverse event which changes CTCAE grade over the course of a given episode will have each change of grade recorded on the adverse event case report forms/worksheets.

If CTCAE grading does not exist for an adverse event, the severity of mild, moderate, severe, and life-threatening, corresponding to Grades 1-4, will be used. Subjects will be monitored by medical histories, physical examinations, and blood studies to detect potential toxicities from the treatment.

Table 6 Evaluating Adverse Events

An investigator who is a qualified physician, will evaluate all adverse events as to:

V5.0 CTCAE Grading	Grade 1	Mild; asymptomatic or mild symptoms; clinical or diagnostic observations only; intervention not indicated.
	Grade 2	Moderate; minimal, local or noninvasive intervention indicated; limiting age-appropriate instrumental ADL.
	Grade 3	Severe or medically significant but not immediately life-threatening; hospitalization or prolongation of hospitalization indicated; limiting self-care ADL.
	Grade 4	Life threatening consequences; urgent intervention indicated.
	Grade 5	Death related to AE
Seriousness	A serious adverse event is any adverse event occurring at any dose or during any use of pembrolizumab that:	
	† Results in death ; or	
	† Is life threatening ; or places the subject, in the view of the investigator, at immediate risk of death from the event as it occurred (Note: This does not include an adverse event that, had it occurred in a more severe form, might have caused death.); or	
	† Results in a persistent or significant disability/incapacity (substantial disruption of one's ability to conduct normal life functions); or	
	† Results in or prolongs an existing inpatient hospitalization (hospitalization is defined as an inpatient admission, regardless of length of stay, even if the hospitalization is a precautionary measure for continued observation. (Note: Hospitalization [including hospitalization for an elective procedure] for a preexisting condition which has not worsened does not constitute a serious adverse event.); or	
	† Is a congenital anomaly/birth defect (in offspring of subject taking the product regardless of time to diagnosis); or	

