7.3.3 Modification of CTC Grading scale for Cytokine Release Syndrome (CRS)

The CTCAE grading system was developed to capture a cytokine release syndrome occurring during infusional therapy and is inadequate to capture the delayed CRS that occurs after CART-19 infusions. We propose to modify the CTC grading specifically to capture toxicity for protocols using CART-19 cells (Table 7.2.5a). Related definitions can be found in **Table 7.2.5b**.

Recipients of CART-19 cells may develop a cytokine release syndrome. Data from small numbers of patients show marked elevations in IL6, IFN-g, and less intensely TNF among other cytokines. Elevations in clinically available markers of inflammation including ferritin and CRP have also been observed to correlate with the clinical CRS syndrome.

Symptoms usually occur 1-14 days after cell infusion, but the syndrome is not defined by the timing of the reaction. Patients developing any symptoms attributable by the investigator as related to cytokine release should be reported as having had a CRS. Symptoms may include:

- High fevers
- Rigors
- Sweating
- Nausea
- Vomiting
- Anorexia
- Fatigue
- Headache
- Myalgia/arthralgia
- Hypotension
- Dyspnea
- Tachypnea
- Hypoxia
- Altered mental status
- End organ dysfunction
- Signs of macrophage activation syndrome including hemophagocytosis and hemolysis

For the purposes of reporting and grading on clinical trials using CART-19 cells, we will use the following grading for CRS Toxicity. The start date of CRS is a retrospective assessment of the date of onset of persistent fevers and/or myalgia consistent with CRS and not explained by other events (i.e. sepsis). The stop date of CRS is defined as the date when the patient has been afebrile for 24 hours and off vasopressors for 24 hours.

This document is confidential and the property of the University of Pennsylvania. No part of it may be transmitted, reproduced, published, or used by other persons without prior written authorization from the regulatory sponsor.

Table 7.2.5a - CRS Toxicity Grading				
1	2	3	4	5

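### Table 7.2.5b is internally inconsistent: dopamine 10 or epinephrine 10 alone is high-dose, but the two together (15 norepinephrine equivalents against a limit of 20) are not, so more pressor support can be graded CRS 3

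*Combined protocol and SAP*

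**What the plan says.** Section 7.3.3 replaces the CTCAE scale for CRS with its own: "For the purposes of reporting and grading on clinical trials using CART-19 cells, we will use the following grading for CRS Toxicity". In Table 7.2.5a, Grade 4 is described as "Life-threatening complications such as hypotension requiring high-dose pressors" or hypoxia needing mechanical ventilation. Grade 3 includes "hypotension requiring multiple fluid boluses for blood pressure support or low-dose pressors". Both pressor entries point to Table 7.2.5b, which defines only high-dose use.

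Table 7.2.5b requires the dose to be held for at least 3 hours. Its single-agent rows are each labelled monotherapy. They include dopamine at 10 mcg/kg/min, epinephrine at 10 mcg/min and phenylephrine at 200 mcg/min. Two further rows cover more than one pressor:

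- The row headed "If on combination vasopressors (not vasopressin" has the limit "Norepinephrine equivalent of ≥ 20 mcg/min (using VASST formula".
- The vasopressin row reads "High-dose if vaso + Norepinephrine Equivalent (NE) of >10 mcg/min".

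A conversion equation follows the table. No line says that an agent meeting its single-agent limit stays high-dose when a second pressor is given.

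The Grade 3/4 boundary is used elsewhere. Under Section 5.2.1.2, CRS of Grades 1 to 3 allows a hold and an optional restart at half dose, whereas "If patients develop grade 4 cytokine release syndrome or require administration of tocilizumab, pembrolizumab will be stopped due to drug toxicity". Section 2.1 names grade 4 CRS in its account of the primary safety endpoint.

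**The concern.** A severity scale should never give a lower grade for more support. The single-agent limits and the combination limits in Table 7.2.5b do not sit at the same level on the table's own scale. A patient on two pressors can therefore fall below the combination limit even though each drug alone would have been high-dose. That patient then meets the Grade 3 pressor wording, if low-dose is taken to mean whatever is not high-dose.

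What is at stake first is the recorded grade of the toxicity the protocol specifically anticipates, since Section 5.4.2 expects that pembrolizumab may re-activate the CAR T cells. Behind that lie the stop-or-restart rule in Section 5.2.1.2 and the toxicity-failure definition in Section 8.1.1.

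**Working it through.** **Inputs**, all from Section 7.3.3: the limits in Table 7.2.5b and the printed equation.

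Norepinephrine equivalent (NE) = norepinephrine + dopamine ÷ 2 + epinephrine + phenylephrine ÷ 10

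**Step 1. Single-agent limits on the NE scale**

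| Agent alone, at its limit | NE | Combination limit |
|---|---|---|
| Phenylephrine 200 | 200 ÷ 10 = 20 | 20 |
| Epinephrine 10 | 10 | 20 |
| Dopamine 10 | 10 ÷ 2 = 5 | 20 |

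Phenylephrine matches the combination limit, so it shows no gap. Epinephrine and dopamine sit well below it. The norepinephrine row is printed per kilogram while the equation is not. That is a separate matter, and none of the examples here depends on it.

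**Step 2. Two pressors, no vasopressin (limit 20 or more)**

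- Dopamine 10 + epinephrine 10: 5 + 10 = 15, not high-dose.
- With dopamine at 10, the second agent must supply 20 − 5 = 15 NE. Anything above 0 and below 15 loses high-dose status. For example, norepinephrine 14 gives 19 (not high-dose) and norepinephrine 15 gives 20 (high-dose).
- With epinephrine at 10, the second agent must supply 20 − 10 = 10 NE. Norepinephrine 9 gives 19 (not high-dose) and norepinephrine 10 gives 20 (high-dose).

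**Step 3. One pressor plus vasopressin (limit above 10)**

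- Dopamine from 10 to 20 gives 5 to 10 NE, not above 10, so not high-dose.
- Epinephrine at exactly 10 gives 10 NE, so not high-dose. This is a single boundary value.

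**Step 4. Who is affected**

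Section 7.3.2 says that an event which changes grade "will have each change of grade recorded on the adverse event case report forms/worksheets". A Grade 4 reached after 3 hours on one agent alone at its limit therefore stays on record when a second drug is added. The gap concerns patients who did not spend 3 hours on one agent alone at its own limit before the second pressor was given. These include:

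- patients started on two pressors together;
- patients given a second pressor before 3 hours at the first agent's limit;
- patients whose first agent ran for longer but below its limit. An example is dopamine 5 for a day, then dopamine 10 with epinephrine 10: the total is 15, and Grade 4 was never reached.

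**Step 5. Effect of the proposed line**

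If an agent at its own limit counts as high-dose whatever else is running, dopamine 10 + epinephrine 10 becomes high-dose. The rule is then met by any of several conditions, none of which can be lost by raising a dose. Adding vasopressin only lowers the NE limit. More support can no longer move a patient from high-dose to not high-dose.

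**The case against.** The strongest reply is that the table is not a closed test. Grade 4 gives high-dose pressors as an example (the wording is *such as*), so an investigator may assign Grade 4 to any life-threatening two-pressor case. Section 10.4 has the medical monitor review grading. Low-dose is never defined, so reading it as the remainder is an inference. All of this stands. A reader might infer that affected patients will be wrongly graded. The documents support only that they could be, if the table is applied mechanically.

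A reader might also infer that the gap changes dosing or the primary safety result. The documents make that remote:

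- Section 5.4.2 directs moderate to severe cases to tocilizumab first, and Section 5.2.1.2 stops pembrolizumab at any grade if tocilizumab is required. Timing is individualised, so a narrow path remains.
- Section 8.1.1 already counts a Grade 3 or higher non-hematologic toxicity that leads to permanent discontinuation as a failure.
- If Section 8.1.1 is read as counting any related CRS, the grade does not affect that count at all.
- The rechallenge note in Table 6 requires advance approval before re-exposure after a serious event that pembrolizumab may have caused.

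Finally, the documents do not show whether the single-agent limits are too low or the combination limit too high. That is fair, and it limits what the fix can claim. None of these points removes the misordering: the section adopts the scale for grading, and reliance on people to override it is a reason to correct it.

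**Conclusion.** The point holds as a minor inconsistency between thresholds in a grading definition. No figure in the protocol is miscalculated. On the NE scale, the dopamine and epinephrine single-agent limits are 5 and 10, against 20 or more for combinations and more than 10 with vasopressin. The reversal covers a second agent worth more than 0 and less than 15 NE with dopamine 10, and more than 0 and less than 10 NE with epinephrine 10. With vasopressin it covers dopamine 10 to 20, and epinephrine at exactly 10.

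This rests on reading the monotherapy rows as applying only to a single agent, which is what the labels say, and on treating low-dose as anything not high-dose. The documents give no rate of pressor-treated CRS after pembrolizumab, so no number of affected patients and no probability of a changed conclusion can be stated.

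**What to change.** Add one line to Table 7.2.5b: *high-dose if any single agent meets its own single-agent limit for at least 3 hours, whether or not other pressors are given, or if the norepinephrine equivalent meets the combination or vasopressin limit.* Apply it prospectively. If past combination-pressor CRS cases are regraded, report both grades and label the regrading post hoc. Regrading can only move grades up, but it would still be a retrospective change to a safety input in an open-label trial of 12 evaluable patients.

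No visit, sample size or analysis changes. There are two costs. Comparability with other CART-19 protocols on the same scale falls slightly. The single-agent limits also remain unequal: dopamine 10 + norepinephrine 1 (5 + 1 = 6 NE) would be high-dose, while epinephrine 9 + norepinephrine 10 (19 NE) would not. Whether to align those limits is for the clinical team.
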